**Figure 3-1      Study design**

Commercially Confidential Information

## **4 Rationale**

### **4.1 Rationale for study design**

The design of this study has been selected to adequately assess the primary objective and follow the similar design of trials for American Psychiatric Association (APA) treatment guidelines for depression ([Practice guideline for the treatment of patients with major depressive disorder 2010](#))

The rationale and justification for the key elements of the study design are as follows:

- Safety of administration of MIJ821 is supported by toxicology studies (i.e. 6-week GLP studies) and by results from a study in healthy volunteers (MIJ821X2101).
- Selection of ketamine 0.5 mg/kg IV infusion is a standard dose shown to have antidepressant effects ([Garay et al 2017](#)).
- Randomization to parallel groups controls for confounding factors and allows for more valid cause judgments.
- Blinding with placebo control limits effects of expectation bias or measurement bias.

The entire treatment period (36 days) can be conducted in an outpatient or inpatient treatment setting. Both settings are commonly used in the treatment of depression and are appropriate for the purpose of the study. The inpatient and outpatient setting in this study includes a frequent visit schedule (weekly). As the outpatient setting may increase the risk of subject suicidality, weekly collections of information about the suicidality risk are implemented.

For the primary objective, the efficacy will be determined using the MADRS ([Montgomery and Asberg 1979](#)) which is a standard for the evaluation of a major depressive episode.

### **4.2 Rationale for dose/regimen and duration of treatment**

Commercially Confidential Information

Commercially Confidential Information

### **4.3 Rationale for choice of control drugs (comparator/placebo) or combination drugs**

The use of placebo saline solution is to provide a comparison group for an unbiased collection and assessment of safety and tolerability data.

Ketamine is included primarily for assay sensitivity and for comparison of side effects. Ketamine is known to be effective with large effect sizes for severe depressive episodes, and it also has high rates of dissociative side effects in 20-30% of subjects, often of moderate to marked severity. It also can cause manic episodes, mixed states, and suicidal or aggressive reactions in a small minority of persons. A single subanesthetic dose of intravenous ketamine consistently decreases symptoms of depression in subjects with treatment-resistant depression in a rapid (within hours), robust (across many symptoms of depression) and relatively sustained (typically, 7–14 days) manner ([Berman et al 2000](#); [Cusin et al 2017](#)). Repeated doses (six infusions over the course of several weeks) have shown promise from an efficacy and safety standpoint ([Aan het Rot et al 2010](#)). The efficacy of two times versus three times a week intravenous ketamine in subjects with treatment-resistant depression in sustaining the initial antidepressant effects was evaluated. Both doses (0.5 and 0.75 mg/kg) were significantly superior to placebo in treating depression symptoms and the transient dissociative side effects attenuated with repeat dosing ([Singh et al 2016](#)). One study examined the benefits of a fixed course of 4 once-weekly ketamine sessions (0.5 mg/kg IV) as continuation phase treatment in 5 patients who had remitted after acute phase treatment. All 5 patients maintained improvement during the continuation phase ([Krystal et al 1994](#)).

To limit any dissociative and psychomimetic side effects, the limiting dose for Ketamine infusion is at 40 mg/infusion for patients over 80 kg.

#### **4.4 Purpose and timing of interim analyses/design adaptations**

Commercially Confidential Information

#### **4.5 Risks and benefits**

There is no expected benefit for subjects participating in the study. However, in instances of documented TRD, participants may benefit from receiving effective antidepressant therapy to treat the MDD.

The risks of participating in the study include those identified in the clinical studies with MIJ821, those associated with IV infusion and those associated with blood sampling. The risk to subjects in this trial may be minimized by compliance with the eligibility criteria, specific procedures done by qualified personnel, study stopping rules as well as close clinical monitoring.

Subjects will be observed for 2-4 hours (i.e. a minimum of 2 hours) after the start of infusion. If they have no dissociative symptoms and no suicidal symptoms after the observation period, they can leave the clinical treatment setting. If investigators judge that subjects have any dissociative symptoms, subjects will be monitored in the clinic until the dissociative symptoms resolve and/or extended stay overnight, or longer based on investigator judgment. If suicidal symptoms are present to a moderate to severe degree, either based on rating scales or investigator judgment, and such symptoms persist throughout the above 2-4 hours monitoring period, investigators may consider extending stay of subjects at least overnight. If suicidal symptoms are mild, either based on rating scales or investigator judgment, the investigator's judgment can be used to allow the subject to leave the clinical setting, but in that case arrangements should be made such that family members or friends are present with the subject for at least 24 hours. If such arrangements cannot be made, the subject may have extended stay at least overnight. If needed, an additional overnight stay beyond the first infusion's baseline and V101 is permissible.

Women of child bearing potential and sexually active males must be informed that taking the study treatment may involve unknown risks to the fetus if pregnancy were to occur during the study, and agree that in order to participate in the study they must adhere to the contraception requirements outlined in the exclusion criteria. If there is any question that the subject will not reliably comply, he/she should not be entered or continue in the study.

Sexually active males must be informed of the requirement to wear a condom for the following reasons:

- Prevent pregnancy in a female partner AND
- Present delivery of investigational drug via seminal fluid to their partner as study treatment may involve unknown risks to the fetus if pregnancy were to occur.

Commercially Confidential Information

Commercially Confidential Information

Given that MIJ821 may impair the mental or physical abilities required for the performance of dangerous potential tasks such as driving a car or operating machinery, subjects should be advised about these potential risks. If the subject is feeling drunk or dizzy or if he/she experiences visual disturbances, hallucinations, or euphoric mood, then the subjects should not drive, use machines or perform any other tasks that require his/her attention and good coordination. In that case, the subject should be hospitalized until resolution of these events. These judgments will be made by the investigators, not the subjects.

In general, hypersensitivity or infusion reaction can manifest with itching, flushing, headache, nausea, vomiting, hypotension, urticaria, bronchospasm, or angioedema. In the event of a hypersensitivity reaction, stop the infusion immediately.

Subjects participating to the MIJ821X2201 study will be provided with a subject information card that they would carry with them at all time and as long as they are treated with MIJ821 or ketamine. This card will warn of potential interaction with CYP3A4, CYP2B6, CYP2C8, CYP2C19, or CYP2D6 inducers or inhibitors and should be presented to every physician/healthcare provider the subject may consult to inform them about potential drug interactions. It is also important that the subject is asked to contact his/her study doctor to inform him/her of his/her status as well as to discuss any treatment recommendations. As a general precaution with all investigational drugs, sites should have the capacity of managing acute hypersensitivity reactions (or similar emergency situations) or be prepared to transfer the subject urgently, should these reactions emerge.

Benefits of ketamine have been shown for rapid improvement of depressive symptoms within 1-2 days, which persists up to 3-4 weeks after one dose. This improvement has been shown mainly with intravenous infusion of 0.5 mg/kg ketamine over 40 minutes ([Katalinic et al 2013](#)). Two open-studies ([Price et al 2009](#), [Thakurta et al 2012](#)) also have suggested that ketamine may be an appropriate treatment to rapidly reduce acute suicide risk in depressed patients. Benefits have been shown also recently with intranasal administration of esketamine. These benefits occur for acute depressive symptoms, and have not been studied or proven for long-term or maintenance administration. The amount of benefit seen acutely meets or exceeds the effect sizes seen with standard antidepressants. Some studies report such benefit in treatment-resistant depression, with patients who have failed multiple prior antidepressant trials. Such benefit has been seen with both bipolar and unipolar depression.

Most of the research conducted using subanaesthetic doses of ketamine has shown psychotomimetic and neuropsychological adverse effects: general psychiatric symptoms, agitation, dissociative symptoms and manic symptoms. These effects have mostly been restricted to the time of administration, disappearing completely by 60 minutes afterward. Other adverse events experienced by patients include feelings of intoxication and lowered inhibitions, confusions, decreased concentration and perceptual disturbances. Most of these

impairments were only apparent during the infusions, and none persisted longer than 2 hours after the beginning of the infusions.

There have been not many significant physical adverse event reported in studies of low-dose ketamine (used as an antidepressant) to date. Some studies have reported a variety of non-permanent physical effects such as light-headedness, headache, nausea, diplopia, drowsiness and dizziness. These symptoms tend to be benign and again limited to the period of the infusion or for a short time following.

Depression trials investigating subanaesthetic doses of ketamine consistently report transient elevations in blood pressure and heart rate during the period of infusion and for up to 80 minutes after dosing.

There have been a number of case reports that have linked repeated ketamine use to urinary tract problems. These cases have mainly been reported in the context of recreational ketamine abuse (where use is chronic, doses are high, and comorbidity with other substance use is common).

Finally, there are concerns about the potential for dependence through long-term or repetitive ketamine use. However, low-dose usage in a medical setting is less likely to produce tolerance ([Katalinic et al 2013](#)).

The above risks will be minimized in this trial by clinical observation during and for 2-4 hours (i.e. a minimum of 2 hours) after the start of infusion period, as well as extended stay if needed based on clinical judgment at any point during the study. If severe dissociative, psychotic, suicidal, or agitated symptoms emerge, clinician-researchers will hospitalize research subjects until those clinical adverse events are resolved. If they persist, or based on clinician-researcher judgment or patient preference, those subjects can be dropped from the study as well at any time. Certain benzodiazepines, specifically lorazepam or alprazolam (as authorized by country), administration also is allowed in the study, within dosage limitations, to manage such possible agitation-related effects of ketamine.

The risk of collecting blood may include fainting, pain and/or bruising: rarely, these may be a small blood clot or infection at the site of the needle puncture. The risks with an IV infusion may include pain, swelling, redness or infection at the injection site. The risk is mitigated by selecting professional staff from the clinic experienced in making this type of infusion.

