#### **6.2.3.2 Other restrictions**

If the subject is feeling drunk or dizzy or if he/she experiences visual disturbances, hallucinations, or euphoric mood, then the subject should not drive, use machines or perform any other tasks that require his/her attention and good coordination.

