#### **9.1.4 Study stopping rules**

The study will be stopped, and no further enrollment will take place pending a full safety review, if any of the following criteria are met:

- At least 5 subjects in any single treatment arm experience an AE of Grade 3 or higher according to the CTC-AE V5.0 and is potentially related to study treatment
- Two or more treatment-emergent SAEs, except those that are clearly and incontrovertibly due to extraneous causes;
- The Sponsor considers that the number and/or severity of AEs justify putting the study on hold.

The study may resume following the safety review, if the Investigator and Sponsor agree it is safe to proceed.

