### **10.1.2 Serious adverse events**

An SAE is defined as any adverse event [appearance of (or worsening of any pre-existing)] undesirable sign(s), symptom(s) or medical conditions(s)) which meets any one of the following criteria:

- fatal
- life-threatening

Life-threatening in the context of a SAE refers to a reaction in which the subject was at risk of death at the time of the reaction; it does not refer to a reaction that hypothetically might have caused death if it were more severe (please refer to the ICH-E2D Guidelines).

- results in persistent or significant disability/incapacity
- constitutes a congenital anomaly/birth defect
- requires inpatient hospitalization or prolongation of existing hospitalization, unless hospitalization is for:
  - routine treatment or monitoring of the studied indication, not associated with any deterioration in condition.
  - elective or pre-planned treatment for a pre-existing condition that is unrelated to the indication under study and has not worsened since signing the informed consent
  - social reasons and respite care in the absence of any deterioration in the subject's general condition
  - treatment on an emergency outpatient basis for an event not fulfilling any of the definitions of a SAE given above and not resulting in hospital admission
- is medically significant, e.g. defined as an event that jeopardizes the subject or may require medical or surgical intervention to prevent one of the outcomes listed above

Medical and scientific judgment should be exercised in deciding whether other situations should be considered serious reactions, such as important medical events that might not be immediately life threatening or result in death or hospitalization but might jeopardize the subject or might require intervention to prevent one of the other outcomes listed above. Such events should be considered as "medically significant". Examples of such events are intensive treatment in an emergency room or at home for allergic bronchospasm, blood dyscrasias or convulsions that do not result in hospitalization or development of dependency or abuse (please refer to the ICH-E2D Guidelines).

Any suspected transmission via a medicinal product of an infectious agent is also considered a serious adverse reaction.

All reports of intentional misuse and abuse of the product are also considered serious adverse event irrespective if a clinical event has occurred.

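### Protocol Section 4.5 directs hospitalisation for foreseen transient symptoms that other passages handle in clinic or by discharge, and nothing says whether such stays count as SAEs towards the two-SAE pause

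*Protocol*

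**What the plan says.** **Hospitalisation.** The paragraph of Protocol Section 4.5 on driving and machinery sets its trigger as "If the subject is feeling drunk or dizzy or if he/she experiences visual disturbances, hallucinations, or euphoric mood". It restricts driving and similar tasks, then adds "In that case, the subject should be hospitalized until resolution of these events". No grade or duration is attached. The next sentence is "These judgments will be made by the investigators, not the subjects".

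**Discharge and clinic stay.** Section 3 and an earlier paragraph of Section 4.5 observe every subject for 2 to 4 hours from the start of infusion. A subject with neither dissociative nor suicidal symptoms may then leave; dizziness is not mentioned. For any dissociative symptoms, Section 4.5 says "subjects will be monitored in the clinic until the dissociative symptoms resolve and/or extended stay overnight", or longer at the investigator's judgment.

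**Severe symptoms.** A later paragraph of Section 4.5 directs hospitalisation when dissociative, psychotic, suicidal or agitated symptoms are severe.

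**Seriousness.** Section 10.1.2 classes an adverse event as serious if it "requires inpatient hospitalization or prolongation of existing hospitalization, unless hospitalization is for" one of four listed reasons.

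**Study pause.** One criterion in Section 9.1.4 is "Two or more treatment-emergent SAEs, except those that are clearly and incontrovertibly due to extraneous causes". Meeting it stops the study and enrolment until a full safety review is done. The study may then resume if the investigator and sponsor agree.

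**Coding.** The adverse-event grouping in SAP Section 7.1.1 places feeling drunk, hallucination and blurred vision under dissociation.

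**The concern.** The same mild, short-lived symptom can lead to discharge, a stay in clinic or hospitalisation, depending on which paragraph a site applies. If the last is recorded as an inpatient admission, the event becomes serious whatever its grade. Three things then depend on the choice of paragraph as well as on the drug: the SAE tables, the 24-hour SAE reporting in Section 10.1.3, and the count that pauses the study.

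The symptoms are foreseen. Section 4.5 introduces the hospitalisation paragraph with a warning about MIJ821, and elsewhere lists feelings of intoxication, perceptual disturbance, double vision and dizziness for ketamine. Although the paragraph opens with MIJ821, investigators are blinded (Section 6.4) and cannot apply it by arm.

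**Working it through.** **Step 1: what each passage directs.**

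| Presentation | Section 3 and early Section 4.5 | Section 4.5, driving paragraph | Later Section 4.5 |
|---|---|---|---|
| Mild dizziness only | May leave after observation | Hospitalise until resolved | Not triggered |
| Feeling drunk or hallucinating, not severe | Clinic and/or extended stay if classed as dissociative (as the SAP does); otherwise may leave | Hospitalise until resolved | Not triggered |
| Severe hallucination | As the row above | Hospitalise until resolved | Hospitalise |

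The first two rows carry incompatible instructions. The SAP grouping is a tabulation rule and does not govern admission, but it shows that the sponsor regards the symptom sets as overlapping.

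**Step 2: does the SAE definition exempt the stay?** The four exemptions in Section 10.1.2 are:

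- routine care of the studied indication: a drug effect after infusion is not the indication;
- elective or planned care of an unrelated pre-existing condition: does not apply;
- social or respite care: does not apply;
- emergency outpatient care without admission: does not apply once the subject is admitted.

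None covers a stay that the protocol itself directs. Section 3 allows subjects who are already inpatients, and for them the prolongation limb could apply. The protocol does not say whether an extended or overnight stay is an inpatient hospitalisation.

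**Step 3: does the SAE count towards the pause?** The two-SAE criterion has no arm, grade or expectedness filter. It excludes only events with clearly extraneous causes, which a post-infusion drug effect is not. By contrast, the Grade 3 criterion in the same section needs at least five subjects in one arm with potentially related events. Two low-grade admissions could therefore pause the study where four subjects in one arm with related, non-serious Grade 3 events would not meet that criterion.

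**Step 4: scale.** The plan states no operating characteristic for the rule, so there is no figure to reproduce. Inputs:

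- n = 66 subjects (Sections 3 and 5);
- threshold 2 (Section 9.1.4);
- p, the chance that a subject has such an admission coded as an SAE during the study. This is not in the documents and is assumed.

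With independent subjects, each counted once:

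P(X ≥ 2) = 1 − (1 − p)^66 − 66 p (1 − p)^65

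At p = 0.01: 1 − 0.51514 − 0.34342 = 0.14144.

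| Assumed p | P(two or more) |
|---|---|
| 0.5% | 4.3% |
| 1% | 14.1% |
| 2% | 38.1% |
| 5% | 84.8% |

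The threshold is 2/66 = 3.0% of subjects. The chance reaches 50% at p of about 2.5%.

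**The case against.** The strongest reply is that actual admissions may be rare. Section 4.5 says ketamine's psychotomimetic effects mostly clear by 60 minutes after administration, that none of the other impairments it describes lasted beyond 2 hours from the start of infusion, and that physical effects such as dizziness are benign and brief. Every subject is already observed for at least 2 hours, so little may remain to admit for. The investigator also has judgment, and the word hospitalised may have been meant as the extended stay described elsewhere. SAE instructions also sit in the investigator folder and the Site Operations Manual, which are not among the documents. All this stands as a limit on the probability. It does not settle which passage governs: the hospitalisation sentence is not confined to symptoms that outlast observation, and judgment without a definition leaves coding to vary by site.

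A reader might infer that Section 6.2.3.2 also contradicts Section 4.5, because for the same symptoms it says only "then the subject should not drive, use machines or perform any other tasks that require his/her attention and good coordination". It does not. It is a restriction addressed to subjects, Section 4.5 contains it too, and the two are compatible.

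A reader might also infer that two admissions would end the trial. Section 9.1.4 provides for a pause that can be lifted after review. A sensitive trigger is a defensible choice in a proof-of-concept study without a data monitoring committee (Section 10.2.4). The objection here is to what feeds the trigger, not to its sensitivity.

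**Conclusion.** The point holds as a conflict among Section 3 and the paragraphs of Section 4.5, together with an undefined status for directed or extended stays under Sections 10.1.2 and 9.1.4. Followed as written, the plan allows two low-grade admissions for foreseen, transient effects to pause the study, and lets SAE counts vary with the passage a site applied. It should be corrected, but it does not threaten the primary analysis.

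The size cannot be estimated from the documents. The 4% to 85% range rests wholly on assumed admission rates of 0.5% to 5%, on independence between subjects, and on every such stay being coded as an SAE.

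It is tempting to go further and say the ketamine arm alone would probably trip the rule, because Section 4.3 cites "high rates of dissociative side effects in 20-30% of subjects". With 66/6 = 11 subjects all admitted at those rates, the chance of two or more would be 0.68 to 0.89. The documents do not support that:

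- the figure is a rate of dissociation, not of admission;
- dissociation has its own disposition in Section 4.5 and is not named in the hospitalisation trigger;
- the allocation is redacted, and with no ketamine arm in the USA, equal allocation within region would give fewer than 11 if any US subjects enrol.

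Nor do they support carrying any such rate over to the MIJ821 arms.

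**What to change.** Reconcile Section 3, the three paragraphs of Section 4.5, Section 9.1.4 and Section 10.1.2 so that these symptoms have one stated disposition. State whether a protocol-directed or extended stay counts as inpatient hospitalisation, or as its prolongation, both for the SAE definition and for the two-SAE count. Which disposition applies is for the sponsor and clinicians to decide; no clinical rule or threshold is proposed here.

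The cost is a wording amendment, approved as Section 14.1 requires, and a communication to sites. Sample size, visits and the efficacy analysis are unaffected.
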